**Table 2-3 Laboratory parameters**

Abnormality	Lab parameter
Hematology	
Anemia	Hemoglobin (g/L)
Platelet count decreased	Platelets (thrombocytes) ( $10^9/L$ )
White blood cell decreased	Leukocytes (WBCs) ( $10^9/L$ )
Neutrophil count decreased	Absolute neutrophil count ( $10^9/L$ )
Lymphocyte count decreased	Absolute lymphocyte count ( $10^9/L$ )
Lymphocyte count increased	Absolute lymphocyte count ( $10^9/L$ )
Chemistry	
Liver function	
Alanine aminotransferase increased	ALT (SGPT) (U/L)
Aspartate aminotransferase increased	AST (SGOT) (U/L)
Blood bilirubin increased	Bilirubin ( $\mu\text{mol/L}$ )
GGT increased	Gamma-glutamyl transferase (GGT) (U/L)
Alkaline phosphatase increased	Alkaline Phosphatase (U/L)

Abnormality	Lab parameter
Renal function	
Creatinine increased*	Creatinine ( $\mu\text{mol/L}$ )
Blood urea Nitrogen (BUN) increased	Urea
INR increased**	International normalized ratio
Lipids	
Cholesterol high	Cholesterol Total ( $\text{mmol/L}$ )
Hypertriglyceridemia	Triglycerides ( $\text{mmol/L}$ )

The number and percentage of participants with new or worsening laboratory abnormalities based on CTCAE grade in each visit-window and at any time post baseline will be presented. Participants with specific laboratory abnormalities (defined by CTCAE grade 3 and 4) will be listed. A case is considered as newly occurring abnormality if the value is not notable or missing at baseline but is notable thereafter. A case is considered as worsening abnormality if the value is notable at baseline and at least one post-baseline value during is worse than baseline.

Shift tables will be provided on CTCAE grades to compare baseline relative to the worst grade. These summaries will be split into hematology and chemistry, and will be presented by treatment group.

Potential drug-induced liver injuries will be evaluated by means of newly occurring liver enzyme abnormalities will also be summarized based on the event criteria given in [Table 2-4](#). A case will be considered as newly occurring if a criterion is not met or missing at baseline but is met thereafter. A case is considered as worsening abnormality if the value is notable at baseline and at least one post-baseline value during is worse than baseline.

For criteria defined by the combination of abnormal parameters in [Table 2-3](#), the identification of cases will be based on a time window between the individual abnormal values of up to end of treatment period. Modified eDISH plots will be generated for potential Hy's law cases.

Liver function tests will also be presented graphically as matrix plots of each of the parameters (ALT, AST, TBL, ALP) maximum post-baseline/upper limit of normal (ULN) normalized.

**Table 2-4**      **Liver enzyme abnormalities**

Parameter	Criterion
ALT	>3xULN; >5xULN; >8xULN; >10xULN, >20xULN
ALT or AST	>3xULN; >5xULN; >8xULN >10xULN; >20xULN
TBL	>1xULN; >1.5xULN; >2xULN; >3xULN
ALP	>1.5xULN; >2xULN; >5xULN
(ALT or AST) & TBL	>3xULN & (TBL>1.5xULN; >2xULN)
(ALT or AST) & INR	>3xULN & INR>1.5
ALP & TBL	>3xULN; >5xULN & TBL>2xUL
(ALT or AST) & TBL & ALP	ALT or AST>3xULN & TBL >2xULN & ALP <2xULN (Potential Hy's Law).

Similarly, participants meeting specific renal alert criteria at any post-baseline will be summarized according to [Table 2-5](#).

**Table 2-5 Specific renal alert criteria**

Parameter	Notable criterion
Serum creatinine	increase 25% – 49% (%change from baseline), increase $\geq$ 50%
Dipstick proteinuria	$\geq$ 3+ (Newly occurring)
Dipstick hematuria (occult blood)	$\geq$ 3+ (Newly occurring)

## 2.7.4 Other safety data

### 2.7.4.1 ECG and cardiac imaging data

ECG data will be collected at scheduled visits in single ECGs or triplicate ECGs. If triplicate ECGs are performed, then average of the non-missing values of the 3 measurements will be used in the analysis. Clinically significant findings from ECG evaluations will be reported as AEs and included in the analysis of AEs. ECG parameters include max heart rate, mean PR duration, mean QT duration, mean QRS duration, and QT corrected using Fridericia's correction formula. Descriptive statistics of each ECG parameter will be provided by treatment group and by visit.

The number and percentage of participants meeting the criteria defined in table below will be provided for each criterion by treatment group and by visit.

Categorical analysis of QT/QTc interval data based on the number of participants meeting or exceeding predefined limits ([Table 2-6](#)) in terms of absolute QT/QTc intervals or changes from baseline will be presented.

All ECG data will be listed by treatment group, participant and visit/time, and abnormalities will be flagged. Summary statistics and graphical presentations (e.g. boxplots) will be provided by treatment and visit/time.

**Table 2-6 Criteria for relevant ECG absolute or change from baseline values**

Absolute values criteria	
QT interval	>500 msec
QTcF:	>450 msec (males) >460 msec (females)
PR:	>200 msec
QRS complex:	>120 msec
Changes from baseline criteria	
QRS complex :	increase >25% compared to baseline
QTcF	increase >60 msec compared to baseline

### 2.7.4.2 Vital signs

All vital signs data will be listed by treatment group, participant, and visit/time and, if ranges are available, abnormalities ([Table 2-7](#)) (and relevant orthostatic changes) will be flagged. Summary statistics and graphical presentations (e.g. boxplots) will be provided by treatment and visit/time.

**Table 2-7 Clinical notable criteria for vital signs**

Vital sign parameter (unit)	Lower bound of clinically notable range	Upper bound of clinically notable range
Notable value considering newly occurring or worsening cases		
Systolic blood pressure (mmHg)	< 90	≥ 140
Diastolic blood pressure (mmHg)	< 60	≥ 90
Pulse rate (bpm)	< 50	> 100
Notable change from baseline		
Systolic blood pressure (mmHg)	≤ 90 and decrease from baseline by ≥ 20	≥ 180 and increase from baseline by ≥ 20
Diastolic blood pressure (mmHg)	≤ 50 and decrease from baseline by ≥ 15	≥ 105 and increase from baseline by ≥ 15
Pulse rate (bpm)	≤ 50 and decrease from baseline by ≥ 15	≥ 120 and increase from baseline by ≥ 15
Weight (kg)	Decrease > 7% from baseline	Increase > 7% from baseline

## 2.8 Pharmacokinetic endpoints

Descriptive statistics of remibrutinib blood concentration data will be provided by treatment arm, and visit/sampling time point, including the frequency (n, %) of concentrations below the LLOQ and reported as zero. Summary statistics will include mean (arithmetic and geometric), SD, CV (arithmetic and geometric), median, minimum, and maximum. Concentrations below LLOQ will be treated as zero in summary statistics and for PK parameter calculations.

Relevant PK parameters will be listed by treatment arm and participant. Descriptive summary statistics for PK parameters will be provided by treatment arm. An exception to this is Tmax where median, minimum and maximum will be presented. PK analysis set will be utilized for all summaries and figures.

## 2.9 PD and PK/PD analyses

The PK and PD properties of remibrutinib and its effect on relevant biomarker changes (SPT) that will impact the clinical endpoints (i.e., responder rate at various peanut allergen doses) will be explored graphically and via longitudinal models (i.e., Mixed model) as appropriate. Details of the modeling plan will be documented in a separate PK/PD analysis plan.

## 2.10 CCI

CCI

CCI

## 2.11 Interim analysis

CCI

## 3 Sample size calculation

The primary objective of this study is to characterize the dose-response relationship among remibrutinib doses (CCI) and placebo with respect to the primary endpoint, responder rate after one month of treatment. The sample size was determined with DesignMCPMod (v0.1.2) application

Approximately 14 completers per remibrutinib 1-month treatment arm and 7 completers on the placebo arm provides at least 80% power (power over the different chosen candidate models assumed) to detect a dose-response relationship for a one-sided alpha of 10%, assuming a true maximum treatment effect of CCI responder rate and placebo treatment effect of CCI responder rate.

CCI

CCI

CCI

Table 3-1

CCI

CCI

## 4 Change to protocol specified analyses

No changes proposed from the protocol specified analyses.

## 5 Appendix

### 5.1 Imputation rules

#### 5.1.1 Study drug

No imputation of missing/partial start or end study drug date. If missing, the time of study end date will be imputed to 00:00:00.

#### 5.1.2 AE date imputation

Rules for imputing the AE end date:

- If the AE end date month is missing, then the imputed end date should be set to the earliest of the study end date, 31DECYYYY or date of death.
- If the AE end date day is missing, then the imputed end date should be set to the earliest of the study end date, last day of the month or date of death.
- If AE year is missing or AE is ongoing, then the end date will not be imputed.

Rules for imputing the AE start date:

1. If imputing end dates, then this should be done prior to calculating imputed start dates.

Before imputing AE start date, find the AE start reference date.

- If the (imputed) AE end date is complete and the (imputed) AE end date < treatment start date, then AE start reference date = min(informed consent date, earliest visit date).
- Otherwise, AE start reference date = treatment start date.

Impute AE start date:

- If the AE start date year value is missing, then the date uncertainty is too high to impute a rational date. Therefore, if the AE year value is missing, then the imputed AE start date is set to NULL.

- If the AE start date year value is less than the treatment start date year value, then the AE started before treatment. Therefore:
  - If AE month is missing, then the imputed AE start date is set to the mid-year point (01JULYYYY).
  - Otherwise, if AE month is not missing, then the imputed AE start date is set to the mid-month point (15MONYYYY).
- If the AE start date year value is greater than the treatment start date year value, then the AE started after treatment. Therefore:
  - If the AE month is missing, then the imputed AE start date is set to the year start point (01JANYYYY).
  - Otherwise, if the AE month is not missing, then the imputed AE start date is set to the later of month start point (01MONYYYY) or AE start reference date + 1 day.
- If the AE start date year value is equal to the treatment start date year value:
  - If the AE month is missing, then the imputed AE start date is set to the AE reference start date + 1 day.
  - If the AE month is less than the treatment start month, then the imputed AE start date is set to the mid-month point (15MONYYYY).
  - Otherwise, if the AE month is equal to the treatment start date month or greater than the treatment start date month, then the imputed AE start date is set to the later of (month start point (01MONYYYY), AE start reference date + 1 day).

If complete (imputed) AE end date is available and the imputed AE start date is greater than the (imputed) AE end date, then imputed AE start date should be set to the (imputed) AE end date.

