### 10.1.2 Adverse events

An adverse event (AE) is any untoward medical occurrence [e.g. any unfavorable and unintended sign (including abnormal laboratory findings), symptom or disease] in a clinical investigation participant after providing written informed consent for participation in the study. Therefore, an AE may or may not be temporally or causally associated with the use of a medicinal (investigational) product.

The investigator has the responsibility for managing the safety of individual participants and identifying adverse events. Novartis qualified medical personnel will be readily available to advise on trial related medical questions or problems.

In general, the occurrence of adverse events must be sought by non-directive questioning of the participants at each visit during the study. Additionally, the investigator should proactively query the participants about the occurrence of specific adverse events related to the administration of study drug, and in the event of accidental food ingestion. Adverse events also may be detected when they are volunteered by the participants during or between visits or through physical examination findings, laboratory test findings, or other assessments.

Adverse events (including lab abnormalities that constitute AEs) should be described using a diagnosis whenever possible, rather than individual underlying signs and symptoms. Adverse events must be recorded under the signs, symptoms, or diagnosis associated with them, accompanied by the following information (as far as possible) (if the event is serious refer to [Section 10.1.3](#)):

1. The severity grade:

- mild: usually transient in nature and generally not interfering with normal activities
- moderate: sufficiently discomforting to interfere with normal activities
- severe: prevents normal activities

2. Its relationship to the study treatment. If the event is due to lack of efficacy the assessment of causality will usually be 'Not suspected.' The rationale for this guidance is that the symptoms of a lack of efficacy are not caused by the trial drug, they happen in spite of its administration and/or both lack of efficacy can only be evaluated meaningfully by an analysis of cohorts, not on a single participant;
3. Its duration (start and end dates) or if the event is ongoing, an outcome of not recovered/not resolved must be reported;

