## 12.5.2 Safety endpoints

For all safety analyses, the safety set will be used. All listings will be presented by treatment group and tables will be presented by treatment arm and overall.

Safety summaries (tables, figures) will include only data from the on-treatment period with the exception of pre-dosing data from Screening Visits 1, 2 and 3 which will also be summarized where appropriate (e.g. change from screening summaries). In addition, a separate summary for death including on treatment and post treatment deaths will be provided. In particular, summary tables for adverse events (AEs) will summarize only on-treatment events, with a start date during the on-treatment period (treatment-emergent AEs).

The on-treatment period lasts from the date of first administration of study treatment (Day 1) to end of treatment.

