## 2.7 Safety analyses

For all safety analyses, the safety set will be used. All listings will be presented by treatment group and tables will be presented by treatment arm and overall. For the 3 weeks Placebo followed by remibrutinib CCI for 1 week arm, the AEs will be listed by the placebo period and remibrutinib period separately to differentiate the AEs that occurred during the respective period.

Safety summaries (tables, figures) will include only data from the on-treatment period with the exception of baseline data from Screening Visits 1, 2 and 3 which will also be summarized where appropriate (e.g. change from screening summaries). In addition, a separate summary for death including on treatment and post treatment deaths will be provided. In particular, summary tables for AEs will summarize only on-treatment events, with a start date during the on-treatment period.

The on-treatment period lasts from the date of first administration of study treatment (Day 1) to 28 days after the end of treatment.

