### 2.7.1 Adverse events (AEs)

All AEs summarized will be displayed by treatment group and overall. All AEs listings will be presented by treatment arm and participant.

All events that the investigator classifies as reactions associated to the DBPCFC or SPT must be captured on the designated eCRF and will not be reported on the AE eCRF. These events will be reported separately and not included in reporting of treatment-emergent AEs (events started after the first dose of study medication or events present prior to start of treatment but increased in severity based on preferred term).

The number (and percentage) of participants with treatment emergent AEs will be summarized in the following ways:

1. by treatment, primary system organ class and preferred term
2. by treatment, primary system organ class, preferred term and maximum severity
3. by treatment, Standardized MedDRA Query (SMQ) and preferred term

Separate summaries will be provided for study medication related AEs, death, serious adverse events (SAEs), and other significant AEs leading to discontinuation. In case of sparse events in any of these categories occur, only a listing will be provided if deemed adequate.

A participant with multiple AEs within a primary system organ class is only counted once towards the total of the primary system organ class.

For the legal requirements of clinicaltrials.gov, two required tables on treatment-emergent AEs which are not SAEs with an incidence greater than a certain threshold based on the final database and on treatment-emergent SAEs and SAEs suspected to be related to study treatment will be provided by system organ class and PT on the safety set population.

If for a same patient, several consecutive AEs (irrespective of study treatment causality, seriousness and severity) occurred with the same SOC and PT:

- a. a single occurrence will be counted if there is  $\leq 1$  day gap between the end date of the preceding AE and the start date of the consecutive AE
- b. more than one occurrence will be counted if there is  $> 1$  day gap between the end date of the preceding AE and the start date of the consecutive AE

For occurrence, the presence of at least one SAE / SAE suspected to be related to study treatment / non SAE has to be checked in a block e.g., among AE's in a  $\leq 1$  day gap block, if at least one SAE is occurring, then one occurrence is calculated for that SAE.

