#### Rules for imputing the CM start date:

If imputing end dates, then this should be done prior to calculating imputed start dates.

- If the CM start date year value is missing, then the imputed CM start date is set to one day prior to Treatment start date (TR01SDT).

- If the CM start date year value is less than the *Treatment start date (TR01SDT)* year value, then the CM started before treatment. Therefore;
- If the CM month is missing, then the imputed CM start date is set to the mid-year point (01JULYYYY).
- Else if the CM month is not missing, then the imputed CM start date is set to the mid-month point (15MONYYYY).
- If the CM start date year value is greater than the *Treatment start date (TR01SDT)* year value, the CM started after treatment. Therefore;
  - If the CM month is missing, then the imputed CM start date is set to the year start point (01JANYYYY).
  - Else if the CM month is not missing, then the imputed CM start date is set to the month start point (01MONYYYY).
- If the CM start date year value is equal to the *Treatment start date (TR01SDT)* year value;
  - And the CM month is missing or the CM month is equal to the *Treatment start date (TR01SDT)* month, then the imputed CM start date is set to one day prior *Treatment start date (TR01SDT)*.
  - Else if the CM month is less than the *Treatment start date (TR01SDT)* month, then the imputed CM start date is set to the mid-month point (15MONYYYY).
  - Else if the CM month is greater than the *Treatment start date (TR01SDT)* month, then the imputed CM start date is set to the month start point (01MONYYYY).

If complete (imputed) CM end date is available and the imputed CM start date is greater than the complete (imputed) CM end date, then imputed CM start date should be set to the complete (imputed) CM end date.

If there is no end date and ongoing check is not ticked, the CM will be considered as ongoing and included in the summary table.

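### Adverse events with no recorded start year get a NULL start date and, read as written, drop out of the treatment-emergent AE, SAE and AESI tables

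*SAP*

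**What the plan says.** SAP 5.1.2 sets an AE start reference date before it imputes anything. The reference is treatment start, unless a complete (possibly imputed) end date falls before treatment start; in that case it is the earlier of consent and first visit. If the month is missing and the year is the treatment year, the start becomes the reference date + 1 day. If the year is missing, the SAP calls the uncertainty too great and states: "if the AE year value is missing, then the imputed AE start date is set to NULL".

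SAP 2.7 says that "summary tables for AEs will summarize only on-treatment events, with a start date during the on-treatment period". It defines the period thus: "The on-treatment period lasts from the date of first administration of study treatment (Day 1) to 28 days after the end of treatment". The protocol's own definition (section 12.5.2) is shorter: "The on-treatment period lasts from the date of first administration of study treatment (Day 1) to end of treatment".

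SAP 2.7.1 defines treatment-emergent events as "events started after the first dose of study medication or events present prior to start of treatment but increased in severity". Neither limb says how an event without a start date is classified.

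Two outputs escape the filter. The AE listings carry no stated start-date restriction (SAP 2.7.1), and SAP 2.7 promises that "a separate summary for death including on treatment and post treatment deaths will be provided".

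**The concern.** Each rule is ordinary on its own. Together they mean that an AE with no start year can never be counted as treatment-emergent, whatever else is known about it. An event with a recorded end date two weeks into treatment is treated like one that ended in screening.

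The result also reverses the SAP's own default. With the month missing and the year known, the event is presumed to have started the day after first dose and is counted. With the year missing as well, the presumption flips to exclusion, and the end date that fixed the reference date is no longer used.

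At stake are the tables of AEs by system organ class and severity, the SAE and drug-related summaries, the AESI table and the registry tables. Within an arm the rule can remove a treatment-emergent event but cannot add one, and the arms are small.

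**Working it through.** The plan gives no figure on this point, so there is nothing to reproduce. Three checks follow.

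**1. How the rules classify each case**

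| AE record | SAP as written | Reference date + 1 day |
|---|---|---|
| Year missing, end date after first dose | not counted | counted |
| Year missing, ongoing | not counted | counted |
| Year missing, end date before first dose | not counted | not counted |
| Month missing, treatment year, end date not before first dose | counted | counted |

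The third row works because the reference for such an event is consent or first visit, and SAP 5.1.2 also caps an imputed start at the end date.

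**2. How uncertain onset really is**

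Inputs:
- Earliest onset: an AE is an occurrence "after providing written informed consent for participation in the study" (Protocol 10.1.2). Screening Visit 1 is 15 to 30 days before Day 1 (Table 8-1), and screening may be extended by one week (Protocol 8.1), giving 15, 30 or 37 days.
- Treatment: nominally 28 days, at most 34 (Protocol section 3).
- Follow-up after last dose: at least 30 days (Protocol 10.1.2), with the safety call up to 5 days later (Table 8-1), giving 30 or 35 days.

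Formulas:
- Span = screening + treatment + follow-up.
- On-treatment share, SAP definition = (treatment + 28) / span.
- On-treatment share, protocol definition = treatment / span.
- Assumption: onsets are evenly spread over the span.

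| Screening + treatment + follow-up | Span (days) | SAP share | Protocol share |
|---|---|---|---|
| 15 + 28 + 30 (shortest span) | 73 | 56/73 = 77% | 28/73 = 38% |
| 30 + 28 + 30 (base case) | 88 | 56/88 = 64% | 28/88 = 32% |
| 15 + 34 + 30 (highest share) | 79 | 62/79 = 78.5% | 34/79 = 43% |
| 37 + 28 + 35 (lowest share) | 100 | 56/100 = 56% | 28/100 = 28% |
| 37 + 34 + 35 (longest span) | 106 | 62/106 = 58% | 34/106 = 32% |

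The span is therefore about 73 to 106 days. The SAP-definition share is 56% to 79%, against the 0% that the NULL rule counts.

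**3. Weight of one event**

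72 participants at 2:2:2:1:1 give 72 × 2/8 = 18 in each one-month remibrutinib arm and 72 × 1/8 = 9 in each of the other two. One participant lost from an AE row moves its incidence by 1/18 = 5.6 or 1/9 = 11.1 percentage points.

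**The case against.** **These cases may never occur.** AEs are sought at every visit of a study lasting about three months. The eCRF has automatic validation checks, missing values are queried, SAEs are reported within 24 hours, and SAE documentation is fully verified (Protocol 10.1.2, 10.1.4, 11.1 to 11.3). This stands and keeps the point minor. It does not make the rule right for an event that does arise.

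**A reader might infer that these events vanish from every output.** The documents do not support that: the listings and the death summary keep them. The exclusion is also the literal result of two rules, not an explicit instruction.

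**A reader might infer that most such events must have started on treatment.** That is not shown. The documents give no AE timing, the share rests on even onset, and 21% to 44% of the span is off treatment even under the SAP definition. Under the protocol definition the on-treatment share is only 28% to 43%. The case for change does not need a majority, since the present rule counts none.

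**The medication rule might look like a precedent.** SAP 5.1.3 says: "If the CM start date year value is missing, then the imputed CM start date is set to one day prior to Treatment start date". It shows that a missing year need not end in NULL, but it places the start before treatment. Applied to AEs it would also put the event outside the on-treatment period, so it gives no support for counting it. The missing-month AE rule is the relevant comparison.

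**The time bound is approximate.** Thirty days is a minimum for AE monitoring, and SAE reporting runs to 30 days after the last study visit, longer for suspected related events (Protocol 10.1.4). This stands in part. The same section sends SAEs after the participant's last visit to the safety database only, not the eCRF.

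**Lost events need not flatter the drug.** True: a lost placebo event would make remibrutinib look worse. The one-way error applies to the count within an arm, not to the comparison between arms.

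**Conclusion.** The point holds as a minor one. SAP 5.1.2 and 2.7, read together and as written, remove AEs with a missing start year from the treatment-emergent AE, SAE and AESI tables, including events whose end date is after first dose. This is a stated rule with the wrong result, and it clashes with the missing-month default in the same section. The stated reason carries little weight when onset is bounded to about 73 to 106 days.

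The 56% to 79% share assumes even onset and the SAP's 28-day extension, so it supports no more than plausibly over half. The likely number of affected events is very small. The reason to act is that one SAE missing from a table matters in arms of 9 and 18.

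**What to change.** In SAP 5.1.2, replace the NULL rule for a missing start year with AE start reference date + 1 day, keeping the existing cap at the end date. The event then counts as treatment-emergent unless its (imputed) end date precedes first dose. Flag these events in the listings.

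Add one line to SAP 2.7 for the delayed-start arm. There the imputed date would be Day 2, inside the placebo period, although the true period is unknown and SAP 2.7 lists that arm's AEs by period. The line should say that such an event is counted in the arm total and listed with period (placebo or remibrutinib) unknown.

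The cost is a sentence or two in each section, before final database lock. The downside is that an occasional pre-treatment event of unknown onset will be counted as treatment-emergent; the listing flag keeps that visible.
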